17.5. Protections against Risk

Every effort will be made to minimize the risks associated with study participation. Experienced research staff will counsel participants prior to enrolment, so that they are aware of the risks described above. All HIV testing will be accompanied by pre- and post-test counselling as per Kenyan national guidelines. In addition, experienced research staff will oversee all computer-

Version 1.1 17 July 2018 Page **72** of **137**

assisted interviews and perform examinations and blood collection. Appropriate clinical and laboratory monitoring will minimize the risk of severe adverse events related to antiretroviral medications during clinic follow-up. Participants will be assured that their clinical care will not be affected by their participation status in any of the aims, nor by their responses in questionnaires. Participants will be enrolled only after written informed consent is given, and have the right to withdraw or refuse an examination or sample collection at any point. We will ask any participant who withdraws from the study to complete a questionnaire regarding his or her reason for withdrawal, care and referral needs, and (if HIV-infected) intent to establish care elsewhere.

In addition, HIV-uninfected partners will all be offered PrEP in this study. Immediate ART and PrEP have both been approved for this study by the Kenyan National AIDS and STD Control Programme (NASCOP), in the context of testing this new intervention. We will stress to participants that this is a pilot program with the goal to detect and manage acute and prevalent HIV infection with the maximum impact on reducing HIV transmission risk. Patients who agree to research follow-up but do not want to initiate ART or PrEP immediately will receive ongoing counselling. Patients who refuse research participation will be offered referral to one of several other HIV clinics in the area and followed as per standard care in Kenya.

Of note, the laboratory test we will use for AHI detection (i.e., the Cepheid *Xpert*® *HIV Qual* assay) has obtained European Conformity in vitro diagnostic (CE-IVD) status in April 2015. For this proposal, we are supported by the Kenyan Ministry of Health in offering immediate ART to all persons with positive *Xpert*® *HIV Qual* results. Therefore, all participants who test positive for AHI will be given post-test counselling, advised to abstain from sex or use condoms, and offered immediate ART. All AHI diagnoses by the *Xpert*® *HIV Qual* assay will be followed up by serial HIV rapid tests at week 2, month 1, month 2, month 3, and month 6. In addition, HIV-1 RNA testing will be conducted at ART initiation and followed every 6 months in the ART cohort.

Staff who participate in the staff interviews or focus group discussions will be informed that their names and identifying information will not be associated with any of the feedback received. They will also be informed of the procedures to protect recordings and transcripts, by keeping these files on an encrypted, password-protected computer only accessible by the research team.

17.6. Potential Benefits of Participation

Although participants in this study may not personally benefit, the following may be considered potential benefits to participants:

- Participants in the stepped wedge trial may benefit from the following:
 - Participants may contribute to and learn from research that will evaluate a unique combination HIV prevention intervention.
 - Participants have access to free diagnosis of AHI through testing that is specific to the research, and would not be included in regular HIV care.
 - Improvement of HIV awareness, diagnostic practices, and clinical care at participating health facilities is a likely side benefit of this research.
 - Diagnosis of acute or prevalent HIV will enable the patient to take measures to avoid infecting their sexual partners and register for HIV care.

- Participants will receive intensive HIV prevention counselling, which includes both sexual risk reduction and ART adherence promotion for participants diagnosed with acute or prevalent HIV.
- Provision of immediate ART to newly diagnosed patients may prevent transmission to their sexual partners and, for women, to their children.
- Provision of PrEP to uninfected partners of HIV-infected individuals may protect them from HIV-1 acquisition.
- Anonymous partner referral services may benefit HIV-infected individuals who do not
 wish to notify partners themselves. In addition, partners of participants will receive
 notification of the exposure to HIV, be counselled about HIV prevention, and be offered
 HIV testing and counseling.
- Staff at the 6 health facilities that participate in the HIV-1 RNA testing intervention trial may benefit from the following:
 - Staff will contribute to and learn from research that will evaluate a unique combination HIV prevention intervention.
 - Staff may have an opportunity to improve HIV awareness, diagnostic practices, and clinical care at their facility.
 - Staff will have the opportunity to provide their views and insights on the value of identifying HIV as early as possible.

Version 1.1 17 July 2018 Page **74** of **137**

18. PUBLICATION POLICY

- Publication of the results of this study will be governed by NIAID and KWTRP publication policies. Any presentation, abstract, or manuscript will be submitted by the Investigator to DAIDS and to the KWTRP Manuscript Review Committee for review prior to submission.
- All publications shall make the following acknowledgement as per the publication
 policy: "Research reported in this publication was supported by the National Institute of Allergy
 and Infectious Diseases of the National Institutes of Health under Award Number
 R01AI124968. The content is solely the responsibility of the authors and does not necessarily
 represent the official views of the National Institutes of Health."
- Following completion of the study, the investigator may publish the results of this
 research in a scientific journal. The International Committee of Medical Journal Editors
 (ICMJE) member journals have adopted a trials-registration policy as a condition for
 publication.

Version 1.1 17 July 2018 Page 75 of 137

19. ADMINISTRATIVE PROCEDURES

19.1. Protocol Registration

Prior to implementation of this protocol, and any subsequent full version amendments, each site must have the protocol and the protocol consent form approved, as appropriate, by their local institutional review board (IRB)/ethics committee (EC) and any other applicable regulatory entity (RE). Upon receiving final approval, sites will submit all required protocol registration documents to the DAIDS Protocol Registration Office (DAIDS PRO) at the Regulatory Support Center (RSC). The DAIDS PRO will review the submitted protocol registration packet to ensure that all of the required documents have been received.

Site-specific informed consent forms (ICFs) WILL be reviewed and approved by the DAIDS PRO and sites will receive an Initial Registration Notification from the DAIDS PRO that indicates successful completion of the protocol registration process. A copy of the Initial Registration Notification should be retained in the site's regulatory files.

Upon receiving final IRB/EC and any other applicable RE approval(s) for an amendment, sites should implement the amendment immediately. Sites are required to submit an amendment registration packet to the DAIDS PRO at the RSC. The DAIDS PRO will review the submitted protocol registration packet to ensure that all the required documents have been received. Site-specific ICF(s) WILL NOT be reviewed and approved by the DAIDS PRO and sites will receive an Amendment Registration Notification when the DAIDS PRO receives a complete registration packet. A copy of the Amendment Registration Notification should be retained in the site's regulatory files.

19.2. Regulatory Oversight

Regulatory oversight will be provided by DAIDS PRO, and local IRB/ethics committee at KEMRI and at the Universities of Washington and Oxford.

19.3. Study Implementation

Pending successful protocol registration and submission of all required documents, DAIDS will "activate" the KEMRI site.

Study implementation may not be initiated until a study activation notice is provided to the KWTRP by the DAIDS PRO. In addition, if study "activation" is determined to be necessary for any subsequent amendments, study implementation may not be initiated until a study activation notice is provided to the KEMRI site by the DAIDS PRO.

19.4. ClinicalTrials.gov

This protocol will be registered in ClinicalTrials.gov.

19.5. Study Coordination

Study implementation will be directed by this protocol as well as the SSP Manual. The SSP Manual will outline procedures for conducting study visits; data and forms processing; social harm assessment, management and reporting; and other study operations.

Study CRFs and other study instruments will be developed by the protocol team. Data will be captured in a Research Electronic Data Capture (REDCap) database for data entry. Data cleaning, reporting and analysis will be done in STATA. Quality control reports and queries will be generated and distributed to the KEMRI site on a routine schedule for verification and resolution.

Close coordination between protocol team members will be necessary to track study progress, respond to queries about proper study implementation, and address other issues in a timely manner. Rates of accrual, adherence, follow-up, and social harm incidence will be monitored closely by the team.

KWTRP staff will address issues related to study eligibility and social harm management and reporting as needed to assure consistent case management, documentation, and information-sharing.

19.6. Study Monitoring

On-site study monitoring will be performed in accordance with DAIDS policies. Study monitors will visit the KEMRI site and study implementation sites to:

- Verify compliance with human subjects and other research regulations and guidelines;
- Assess adherence to the study protocol, study-specific procedures manual, and local counseling practices; and
- Confirm the quality and accuracy of information collected at the study sites and entered into the study database.

Site investigators will allow study monitors to inspect study facilities and documentation (e.g., ICDs, clinic and laboratory records, other source documents, CRFs), as well as observe the performance of study procedures.

Investigators also will allow inspection of all study-related documentation by authorized representatives of NIAID, IRBs/ethics committees, and US regulatory authorities (i.e., the Office for Human Research Protections). A visit log will be maintained at KEMRI to document all site visits.

19.7. Protocol Compliance

The study will be conducted in full compliance with the protocol. The protocol will not be amended without prior written approval by the Protocol Chair and DAIDS Medical Officer. All protocol amendments must be submitted to and approved by the relevant IRB(s) and the DAIDS Regulatory Support Center (RSC) prior to implementing the amendment.

19.8. Investigator's Records

All Investigators of Record (IoR) will be responsible for maintaining, and storing in a secure manner, complete, accurate, and current study records throughout the study. Under HHS regulations, the IoR is required to retain all study records relating to research for at least three [3] years after completion of the research, or longer if needed to comply with local regulations. Completion of a clinical research study occurs when the following activities have been completed:

- All research-related interventions or interactions with human subjects;
- All protocol-required data collection of identifiable private information described in the IRB/ethics committee-approved research plan;
- All analysis of identifiable private information described in the IRB/ethics committeeapproved research plan;
- Primary analysis of either identifiable private or de-identified information.

Study records include administrative documentation (including protocol registration documents and all reports and correspondence relating to the study), as well as documentation related to each

 $Novel\ HIV\text{-}1\ RNA\ testing\ intervention\ to\ detect\ acute\ and\ prevalent\ HIV\ infection\ -\ Tambua\ Mapema\ Plus\ Plu$

participant screened and/or enrolled in the study (including ICDs, locator forms, CRFs, notations of all contacts with the participant, and all other source documents).

Version 1.1 17 July 2018 Page **78** of **137**

21. APPENDICES

21.1. Schedule of Procedures, Observation Period HIV Testing Cohort

SCHEDULE OF PROCEDURES - OBSERVATION PERIOD

Procedures	Visit 1	Visit 2
Visit week	WK0	WK 6 ¹
Date of visit	х	Х
Eligibility Screening	Х	
Informed Consent (Consent 1)	Х	
Contact Information	Х	
Sociodemographic Questionnaire	Х	
Risk Assessment Questionnaire	Х	
HIV Counseling and Testing ²	±	
Assessment of Linkage to Care, ART, Disclosure, and Self- report of Partner HIV Status ³		Х
Offer Standard Assisted Partner Services (aPS) if Eligible (Consent 3) ³		Х

- 1) Week 6 procedures will be conducted for HIV-positive participants only.
- 2) HIV testing will be performed at the discretion of the health facility provider, using standard rapid antibody tests to confirm prevalent (i.e., seropositive HIV status) in accordance with current Kenyan Ministry of Health testing guidelines.
- Standard aPS uses standard rapid antibody tests to confirm prevalent (i.e., seropositive HIV status) in accordance with current Kenyan Ministry of Health testing guidelines

Version 1.1 17 July 2018 Page 83 of 137

21.2. Schedule of Procedures, Intervention Period POC HIV-1 RNA Testing Cohort

SCHEDULE OF PROCEDURES - INTERVENTION PERIOD

Procedures	Visit 1	Visit 2
Visit week	WK0	WK 6 ¹
Date of visit		
Eligibility Screening	X	
Informed Consent (Consent 2)	X	
Contact Information	X	
Sociodemographic Questionnaire	X	
Risk Assessment Questionnaire	X	
HIV Counseling and Testing ²	X	
Intimate Partner Violence Assessment ³	X	
Offer Enhanced Assisted Partner Services if Eligible (Consent 3) ³	Х	
Offer ART Cohort Enrolment (Consent 5)3	X	
Sample storage	X	
Assessment of Linkage to Care, ART, Disclosure, and Self-Report of Partner HIV Status ³		Х
Total Blood Volume per Visit (mL)	4	

- 1) Week 6 procedures will be conducted for HIV-infected participants only.
- 2) HIV testing will be performed with X-pert testing, followed with rapid antibody tests in RNA positive samples to confirm prevalent (i.e., seropositive HIV status).
- 3) Only for HIV-infected patients (both AHI and prevalent cases). Enhanced aPS includes POC X-pert HIV-1 RNA testing, followed with rapid antibody tests in RNA positive samples to confirm prevalent (i.e., seropositive HIV status).

Version 1.1 17 July 2018 Page **84** of **137**

21.3. Schedule of Procedures, Partner Testing

SCHEDULE OF PROCEDURES for PARTNER TESTING – OBSERVATION AND INTERVENTION PERIODS

Procedures	Visit 1	Visit 2
Visit week	WK0	WK 6 ¹
Date of visit		
Confirmation of partner's identity	X	
Informed Consent (Consent 4)	X	
Contact Information	X	
Sociodemographic Questionnaire	X	
Risk Assessment Questionnaire	X	
HIV Counseling and Testing ²	Х	
Intimate Partner Violence Assessment ³	Х	
Offer Assisted Partner Services if Eligible (Consent 3) ³	X	
Offer ART Cohort Enrolment if HIV Positive (Consent 5) ⁴	X	
Offer PrEP Cohort Enrolment if HIV Negative (Consent 6) ⁴	Х	
Sample storage ⁴	X	
Assessment of Linkage to Care, ART, Disclosure, and Self-Report of Partner HIV Status ³		х
Total Blood Volume per Visit (mL)	4	

- 1) Week 6 procedures will be conducted for HIV-infected partners only.
- 2) In the observation period, HIV testing will be performed with standard rapid antibody tests to confirm prevalent (i.e., seropositive HIV status). In the intervention period, HIV testing will be performed with standard rapid antibody tests when tested at home or another private location, and with X-pert testing, followed with rapid antibody tests in RNA positive samples to confirm prevalent (i.e., seropositive HIV status) when tested at the research clinic.
- Only for HIV-infected partners in the intervention period
 Only for partners of patients in the intervention period

Page 85 of 137 Version 1.1 17 July 2018

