11.1.4. Recruitment of Partners

Partners identified through the aPS intervention will be offered HIV testing
according to the period in which the associated index patient was diagnosed (i.e.,
standard rapid HIV tests in the observation period, testing for both acute and
prevalent HIV infection in the intervention period).

Version 1.1 17 July 2018 Page 30 of 137

- During the intervention period, partners who are newly diagnosed with HIV will be
 offered enrolment in the ART cohort at the nearest KEMRI Research Clinic and will
 also be offered participation in the enhanced aPS intervention.
- In this same period, partners who are uninfected and in an ongoing serodiscordant partnership will be offered enrolment in the PrEP cohort at the nearest KEMRI Research Clinic.
- Consent 4 will be used for enrolment of partners for standard HIV testing (observation period) or for the HIV-1 RNA testing intervention (intervention period).
- Consent 5 will be used for enrolment of partners into the ART cohort, and Consent 6 will be used for enrolment of partners into the PrEP cohort

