11.4.3. Partners of Index Cases Who Consent to APS

- The schedule of procedures for partner testing is detailed in Appendix 21.3.
- When notifying partners, research staff will counsel the partner about HIV and encourage them to test at the nearest KEMRI Research Clinic.
- Partners who are successfully contacted in person will be given a study card with a
 unique ID number linked to the index case's unique ID number to present at the
 nearest KEMRI Research Clinic.
- If contact is established by telephone and the partner agrees to come to the VCT site
 at the nearest KEMRI Research Clinic for HIV-testing, we will send an SMS with an
 ID number linked to the index case's unique ID number, to be used when the partner
 presents for HIV testing.
- Partners who agree to testing in this study will undergo informed consent using an
 informed consent document (ICD) developed for this purpose (Consent 4). If a
 partner refuses to participate in the research study, he or she will be offered VCT in a
 non-research context (i.e., without data collection).
- After consent, the same CASI/CAPI used in the stepped wedge trial (described in section 11.2) will be administered, in order to capture demographic and sexual risk behavior data from participating partners.
- After the CASI/CAPI, the partner will then undergo HIV testing, using standard rapid HIV tests (i.e., standard aPS) for partners of observation period index patients and using the HIV-1 RNA testing intervention (i.e., enhanced aPS) to detect acute and prevalent HIV infection for partners of intervention period index patients.
- If a partner refuses to come to the clinic but consents to enrolment and HIV testing at home, field staff will conduct rapid HIV testing in the home and note the result. For partners of intervention period index patients, blood collected at the partner's home will be transported to the nearest KEMRI Research Clinic laboratory for the XPert®

- HIV Qual test. Field staff will provide these results to intervention period partners within 48 hours and offer further research options (i.e., ART or PrEP cohort enrolment, enhanced aPS if HIV-infected) or referral to HIV prevention services or care as indicated.
- Partners of observation period index patients who are found to be seropositive will
 be offered referral to the local HIV care facility of their preference and will not be
 eligible for the ART cohort at the KEMRI Research Clinics. Partners who test

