12.1.3. HIV Testing for Identified Partners in the aPS Intervention

- All identified partners of index patients diagnosed in the observation period will be tested with standard HIV rapid tests, in accordance with Kenyan guidelines.
- All identified partners of index patients diagnosed in the intervention period will undergo the same screening laboratory tests as described for HIV testing in the intervention period.

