Assisted partner	Assisted partner services consent	N=75 / 6 health facilities or KEMRI	
notification	for all newly diagnosed	clinic	
4. Partner testing	Partner testing consent	N=300 / partner home or KEMRI	
		clinic	

Version 1.1 17 July 2018 Page **70** of **137**

5. Immediate	Cohort follow-up for HIV positive	N= 75 (and unknown HIV infected
treatment	patients and partners	partners) / KEMRI clinic
6. PrEP	Cohort follow-up for HIV negative (with PrEP)	N=75 / KEMRI clinic
7. Qualitative	Personal interview	N=60 / KEMRI clinic
8. Staff	Personal interview or focus group	N=60 / 6 health facilities

- Each ICD document will describe the purpose of the specific component of the study described, the procedures to be followed, and the risks and benefits of participation.
- During the consent process with each ICD, staff will explain the purpose and design of the specific study component, taking care to inform patients that participation is voluntary and will not influence their access to care or any other services to which they are entitled.
- Consent forms will be available in Swahili and English, and a copy will be given to each
 participant in the language of his or her choice.
- If an individual is illiterate, we will explain all procedures, risks, and benefits and offer the
 option of having a friend, family member, or paid consultant who is not a member of the
 research staff be present to further explain the study.
- Written informed consent will be obtained from all participants; persons incapable of consenting are excluded.
- Potential participants who would like to take additional time to consider their enrolment will be encouraged to do so.
- The informed consent process will be conducted by staff members trained in the ethical treatment of human subjects. This process involves presenting a detailed verbal description of the study as described on the printed, IRB-approved consent form.
- Staff will emphasize that participation is voluntary, and that participants can refuse to answer
 any question or undergo any procedure or can discontinue participation at any time without
 penalty.
- Participants will be informed of the procedures for ensuring confidentiality, including use of
 unique non-personally identifying ID numbers instead of names on research materials, and the
 maintenance of data in encrypted computer databases and locked filing cabinets in locked
 rooms.

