21.5. Schedule of Procedures, PrEP cohort SCHEDULE OF PROCEDURES, PREP COHORT

Procedures	Visit 1	Visit 2	Visit 3	Visit 4	Visit 5	Visit 6	Visit 7	Visit 8	Visit 9	Visit 10	Visit 11	Visit 12	Visit 13	Visit 14
Visit Month (Study Month = 28 days)	MO	WK 2	M1	M2	М 3	M4	М5	М6	М7	М8	М9	M10	M11	M12
Date of visit														
Eligibility Screening	Х													
Informed Consent (Consent 6)	Х													
Contact Information	Х	Х	Х	Х	Х	Х	Х	Х	X	Х	Х	Х	Х	Х
Sociodemographic Questionnaire	Х													
Risk Assessment Questionnaire	Х				Х			Х			Х			Х
HIV Counseling and Testing ¹	Х		Х		Х			Х			Х			Х
Intimate Partner Violence Assessment	Х				Х			Х			Х			Х
Risk Reduction Counselling	Х	Х	Х	Х	Х	Х	Х	X	X	X	Х	Х	Х	Х
Mental Health Assessment	Х													Х
Medical History	Х				Х			Х			Х			Х
Physical Exam, including collection of vaginal and/or rectal swabs as indicated	х				х			х			х			Х
Hepatitis B vaccination ²	Х		Х					Х						
Qualitative Interview (if consented for this procedure, Consent 7)		х			Х			Х			Х			Х
PrEP Initiation and Refills ³		Х	Х	Х	Х	Х	Х	Х	Х	Х	Х	Х	Х	Х
PrEP Adherence Counselling ³	Х	Х	Х	Х	Х	Х	Х	Х	Х	Х	Х	Х	Х	Х
PrEP Adherence Evaluation ³		Х	Х	Х	Х	Х	Х	Х	Х	Х	Х	Х	Х	Х
Urine Pregnancy Test (women only) ⁴	х	Х	Х	Х	Х	Х	х	х	Х	Х	Х	Х	Х	Х
Urinalysis	Х													Х
Urine collection for STI testing (men only)	Х				Х			Х			Х			Х
Hepatitis B Surface Antigen	Х													

Version 1.1 17 July 2018 Page 88 of 137

Procedures	Visit 1	Visit 2	Visit 3	Visit 4	Visit 5	Visit 6	Visit 7	Visit 8	Visit 9	Visit 10	Visit 11	Visit 12	Visit 13	Visit 14
RPR with TPHA if Positive	X													X
Creatinine	Х		Х		Х			X						X
Sample storage	Х		Х		Х			X			Χ			Χ
Total Blood Volume per Visit (mL)	10	0	4	0	8	0	0	8	0	0	8	0	0	10

- 1. HIV testing will be performed with standard rapid antibody tests at all visits. At baseline, HIV testing will include X-pert® HIV Qual testing to test for AHI.
- 2. HBV vaccination (with doses at baseline, month 1, and month 6) should be provided if at high risk for HBV transmission (i.e., FSW, MSM, or male sex worker), as evaluated by the Risk Assessment Questionnaire administered at the baseline and follow-up visits as above.

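### The partner-testing schedule conflicts with the body of the protocol on whether intervention-period partners tested at home get an RNA test, which puts the secondary partner-AHI count at risk of being biased low

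*Combined protocol and SAP*

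**What the plan says.** Four places in the protocol describe HIV testing for partners of index patients diagnosed in the intervention period.

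- **Appendix 21.3, footnote 2** splits testing by place. It says "In the intervention period, HIV testing will be performed with standard rapid antibody tests when tested at home or another private location", and then gives Xpert, followed by rapid tests on RNA-positive samples, for testing at the research clinic.
- **Section 11.4.3** covers the home case directly: "If a partner refuses to come to the clinic but consents to enrolment and HIV testing at home", field staff do a rapid test there. For intervention-period partners the blood also "will be transported to the nearest KEMRI Research Clinic laboratory for the XPert" assay, with results returned within 48 hours.
- **Section 12.1.3** says that all identified partners of intervention-period index patients "undergo the same screening laboratory tests as described for HIV testing in the" intervention period, which means RNA first.
- **Section 11.1.4** assigns the test by the period of the index patient, not by place: "standard rapid HIV tests in the observation period, testing for both acute and" prevalent infection in the intervention period.

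Home testing is a planned route. The consent table in Section 17.3 lists partner testing as "N=300 / partner home or KEMRI" clinic. The number of partners newly diagnosed with AHI is a week 6 secondary endpoint in Section 5 and again in Section 15.3, and it is taken as 0 in the observation period.

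**The concern.** Section 7.1 defines AHI as RNA-positive with seronegative or discordant rapid tests. Without an RNA result the definition cannot be met. If the footnote is followed, a partner tested at home who has AHI and is seronegative is recorded as negative, and one with discordant rapid tests is not classified as AHI. Seropositive partners are still counted as prevalent cases.

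The partner-AHI count would then depend on where partners happened to be tested. Home-tested partners would get the same kind of test as observation-period partners, which weakens the comparison in Section 6.3 between RNA-based and rapid-test partner services. Section 15.4 takes the effect of enhanced partner services from study data, so a shortfall would carry into the model. If location and test type are not recorded, an analyst could not tell an absence of partner AHI from an absence of RNA testing.

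**Working it through.** **1. Compare the texts.**

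| Source | Home-tested partner, intervention period | RNA test? |
|---|---|---|
| Appendix 21.3, footnote 2 | Rapid antibody tests; Xpert named only for the research clinic | No, on its natural reading |
| Section 11.4.3 | Rapid test at home, blood transported for Xpert | Yes |
| Section 12.1.3 | Same tests as intervention-period participants | Yes |
| Section 11.1.4 | Testing for acute and prevalent infection, by index period | Yes |
| Appendix 21.2, footnote 3 | Enhanced partner services include Xpert, no home exception | Yes |

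The footnote is the outlier.

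**2. Ask whether a missed case would be found later.** Week 6 procedures are only for HIV-infected partners (Appendix 21.3, footnote 1). Under Section 8, HIV-negative partners who decline the PrEP cohort leave the study at baseline. The scheduled later RNA test is at PrEP-cohort entry: "At baseline, HIV testing will include X-pert® HIV Qual testing to test for AHI" (Appendix 21.5, footnote 1). That cohort is restricted: "partners who are uninfected and in an ongoing serodiscordant partnership will be offered enrolment in the PrEP cohort at the nearest KEMRI" clinic. Home testing is for partners who refused to come to the clinic, so recovery may be least likely in this group.

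**3. Reproduce the plan's own partner figure.** Section 14 assumes 150 partners tested (30 of AHI patients and 120 of prevalent patients) at 48.0% prevalence, with limits of 39.8% to 56.3%. Exact binomial limits for 150 × 0.48 = 72 of 150 are 39.78% to 56.30%. The figure reproduces and is not in dispute.

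**4. Illustrate the loss.** Let N be partners tested, a the AHI prevalence among them, h the share tested at home and r the share of missed cases RNA-tested later. With equal AHI prevalence at home and clinic:

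- cases not diagnosable at the home test = N × a × h
- cases finally missed = N × a × h × (1 − r)
- share of partner AHI missed = h × (1 − r)

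N = 150 is from Section 14. The documents give none of a, h or r. The assumed values are a = 2–5%, h = 25–50%, and r = 0, 0.5 or 1.

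- True cases: 150 × 0.02 = 3 to 150 × 0.05 = 7.5.
- Not diagnosable at the home test: 3 × 0.25 = 0.75 to 7.5 × 0.50 = 3.75.

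| Share RNA-tested later (r) | Cases finally missed | Share of partner AHI missed |
|---|---|---|
| 0 | 0.75–3.75 | 25–50% |
| 0.5 | 0.375–1.875 | 12.5–25% |
| 1 | 0 | 0% |

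Wider assumptions (a = 1–10%, h = 10–50%, r = 0–0.5) give a loss of 0.10 × 0.5 = 5% to 0.50 × 1 = 50%. In cases this is 150 × 0.01 × 0.10 × 0.5 = 0.075 to 150 × 0.10 × 0.50 × 1 = 7.5.

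**5. Compare with all partner diagnoses.** Against 72 partner infections, the r = 0 loss under the main assumptions is 0.75/72 = 1.0% to 3.75/72 = 5.2%. At the extreme of the wider set it is 7.5/72 = 10.4%. The loss falls mainly on the AHI count and on what RNA testing adds, not on total partner diagnoses.

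**The case against.** The best defence is that the footnote describes where each assay is run: the rapid test in the home, and Xpert at the clinic on blood brought there. That would agree with Section 11.4.3. The footnote does not say that home partners get rapid tests only, Section 11 calls the schedules an overview, and detailed instructions are left to the study-specific procedures manual. Appendix 21.3 itself lists 4 mL of blood at the first visit and sample storage for intervention-period partners, with no home exception, and 4 mL is the volume drawn for Xpert, rapid tests and storage. Loose wording is therefore plausible.

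That reading is open but strained. The footnote's clinic branch already contains its own rapid tests after a positive RNA result, so the two branches read as complete testing sequences chosen by where the partner is tested. It never mentions transported blood. A manual outside the documents cannot cure a contradiction inside the protocol.

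Three further points stand in part. First, discordant rapid results at home are visible and could prompt retesting, so the r = 0 losses are too high by an unknown amount. Second, the illustrated loss only restates assumed inputs. Third, Section 16.2 already links barcoded rapid and Xpert kits to each participant, which covers part of the recording request, though not test location.

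**Conclusion.** The concern holds. The contradiction is textual and needs no assumption: footnote 2 of Appendix 21.3 does not match Sections 11.4.3, 12.1.3 and 11.1.4. That no AHI can be diagnosed at the home test under the footnote's natural reading follows from the protocol's own definition. The resulting bias is conditional on staff following the footnote and on at least some affected partners never being RNA-tested. Its size is unknown. Under the main assumptions it ranges from none to half of partner AHI.

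One secondary endpoint is affected, together with the estimate of what RNA testing adds to partner services. The primary endpoints and the power table concern trial participants and are unaffected. This should be corrected, but it does not threaten the main result.

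**What to change.** - Reconcile footnote 2 of Appendix 21.3 with Sections 11.4.3, 12.1.3 and 11.1.4 so that a single testing rule covers intervention-period partners wherever they are tested.
- Record for each partner the test location, the tests done and the date of any later RNA test.
- In Section 15.3, report the number of partners with an RNA result, by test location, beside the partner-AHI count.

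The cost is one footnote, a few case report form fields (partly covered by the barcode log) and one reporting sentence. Transport of home-collected blood for RNA testing is already described in Section 11.4.3.
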